13.3 Review of Reported Events

The Sponsor will review the investigator's assessment of all reported events submitted to determine and document in writing their seriousness and relationship to the study device and related procedures required by this protocol. In case of disagreement, the sponsor will consult the investigator for clarification and correction if required. If the disagreement cannot be resolved, the Sponsor shall communicate both opinions to the Post Market Surveillance team for further investigation and required reporting if applicable.

13.4 Intensity of Symptoms

13.4.1 Mild

The subject is aware of the sign or symptom, but finds it easily tolerated. The event is of little concern to the subject and/or little clinical significance. The event is not expected to have any effect on the subject's overall health or well-being.

13.4.2 Moderate

The subject has discomfort enough to cause interference with or a change in usual activities. The event is of some concern to the subject's health or well-being and may require medical intervention and/or close follow-up.

13.4.3 Severe

The event interferes considerable with the subject's usual activities. The event is of definite concern to the subject and/or poses substantial risk to the subject's health or well-being. The event is likely to require medical intervention and/or close follow-up and may be incapacitating or life threatening. Hospitalization and treatment may be required.

Note: The term "severe" refers to the intensity of the event and can be used with any event, without regard to whether or not it meets the criteria for being classified as "serious" or "unanticipated". For example, a subject can have a severe headache, but it is not a serious event.

13.5 Outcome Definitions

The outcome is reported in relationship to the Adverse Event, not the treatment rendered for the event (if any).

13.5.1 Resolved

This outcome indicates the event has improved or recuperated.

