12.4.8 Adverse Events

See Safety Management – Medical Events/Adverse Events Section of this protocol for additional information regarding adverse event classifications.

Reporting and Documentation of Adverse Events and Adverse Device Effects

Adverse Events and Adverse Device Effects have to be documented ideally including information on the type of event, date of onset, treatment and resolution, as well as assessment of both the seriousness and the relationship to the study device, instrumentation and/or procedure. Further, the outcome of complications has to be documented and summarized in the final report. In case of early termination of the study, further follow-up of the patient shall proceed according to the hospital's standard procedure.

Reporting and Documentation of Serious Adverse Events, Serious Adverse Device Effects, and Device Deficiencies

Serious Adverse Events and **Serious Adverse Device Effects** have to be **reported to the Sponsor as soon as possible**. The incidence has to be documented over the whole time of the investigation ideally including information on the type of event, date of onset, treatment and resolution, as well as assessment of both the seriousness and the relationship to the study device, instrumentation and/or procedure based on the evaluation of the investigator. The outcome of such complications has to be documented and summarized in the final report. In case of early termination of the study, further follow-up of the study subject shall proceed according to the hospital's standard procedure.

Device Deficiencies that did not lead to an adverse event but **could have led** to a medical occurrence if suitable actions had not been taken, if intervention had not been made or if circumstances had been less fortunate shall be **reported to the Sponsor as soon as possible**, as well.

The **Investigator** is responsible for reporting all SAEs, SADEs, USADEs and Device Deficiencies that could have led to a SADE to the Ethics Committee if required by national regulations or by the EC.

13 Safety Management – Medical Events/Adverse Events

Adverse events are required to be summarized in the final report.. The Investigator or Designee will also promptly provide the Sponsor with any additional requested information required for the Sponsor to comply with regulatory requirements. If applicable per their reporting requirements, the Investigator or Designee will also report applicable adverse event(s) to their EC.

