13.5.2 Resolved with Sequelae

This outcome indicates the subject recuperated but retained pathological conditions resulting from the prior disease or injury.

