13.5.3 Resolving*

This outcome indicates that the event is improving.

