13.5.4 Not Resolved*

This outcome indicates that the adverse event has not improved or recuperated.

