13.5.6 Unknown*

The outcome of the adverse event is not known, not observed, not recorded, or patient refused to provide information to make an outcome determination.

*Per Regulation (EU) 2017/745 [3], all serious adverse events will be classified according to event status outlined in MDCG 2020-10/1 [4] when used to support MDR reporting requirements. These event statuses include Resolved, Resolved with Sequelae, Death,

and On-going. In order to comply with this reporting requirement, all serious adverse events or Device Deficiency (DD) with outcomes classified as 'Resolving', 'Not Resolved', or 'Unknown', will be reclassified as 'On-going' and all serious adverse events classified as 'Fatal' will be reclassified as 'Death'.

14 Monitoring

Prior to initiating the clinical study, the Sponsor may conduct a site evaluation visit to ensure the Investigator and study staff understands the study protocol and requirements and have adequate time and resources to implement and conduct the study. Prior to study initiation, EC approval and a fully executed CTA must be in place.

This is a post-market study that does not involve investigational products or procedures, and there is no physical risks to the patients to be included in the study. Many assessments, such as the Harris Hip Score were used as standard-of-care for this patient population and do not require special training for their use in the study. As such, site initiation visits may be conducted remotely for this study.

During the course of the study, the Sponsor would conduct periodic central monitoring if necessary and maintain contact with the study staff to monitor compliance and evidence of adverse events, in accordance with the Sponsor's policies and procedures. The Sponsor will address any identified non-compliance with the executed CTA, study protocol, and applicable regulatory requirements.

If onsite monitoring visit(s) are deemed appropriate by the Sponsor, the Investigator will permit representatives of the Sponsor's monitoring team to have direct access to inspect all source data/documents, study documents/binders, study subject forms, database, corresponding sections of study subject medical/hospital records, and any other documents relevant to the study.

Additional details are provided in the Monitoring plan.

15 Risk Analysis

A discussion of the different types of risks and benefits involved with participation in the investigation, including, but not limited to:

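### Section 13.5.1 lets an adverse event that has only improved be coded *Resolved*, so one partly recovered serious event can be reported as *Resolved* or *On-going*

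*Combined protocol and SAP*

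**What the plan says.** Section 13.5 gives six outcome codes. Four matter here:

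- *Resolved* (13.5.1): "This outcome indicates the event has improved or recuperated".
- *Resolved with Sequelae* (13.5.2): "This outcome indicates the subject recuperated but retained pathological conditions resulting from the prior disease or injury".
- *Resolving* (13.5.3): "This outcome indicates that the event is improving".
- *Not Resolved* (13.5.4): "This outcome indicates that the adverse event has not improved or recuperated".

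The other two are *Fatal* and *Unknown*. The note at the end of 13.5.6 converts these codes to regulatory statuses where the data feed MDR reporting. It says "These event statuses include Resolved, Resolved with Sequelae, Death", and adds *On-going* as the fourth. For serious adverse events and device deficiencies, "outcomes classified as 'Resolving', 'Not Resolved', or 'Unknown', will be reclassified as 'On-going". *Fatal* becomes *Death*. *Resolved* is carried over as it stands.

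Section 12.4.8 makes the outcome a reported item. For adverse events and device effects in general, "the outcome of complications has to be documented and summarized in the final report". It repeats the requirement for serious events: "The outcome of such complications has to be documented and summarized in the final report".

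**The concern.** An outcome code should put each event in one category, and *Resolved* would ordinarily mean that the event is over. In 13.5.1 improvement and recuperation are alternatives, so an event that is better but still present qualifies. Nothing in section 13.5 requires the event to have ended, and nothing says which code prevails when two apply.

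Two things are at stake. The outcome summary in the final report could list persisting complications as resolved. And the status of a serious event in MDR reporting could depend on which definition the person reading the chart happened to use.

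The written definitions carry much of the weight here. Outcomes are coded retrospectively from charts of operations done between 2010 and 2018 (10.5). The investigator's team manages the data (12.2.5), and the database stays at the hospital (12.2.1, 12.2.2). The sponsor's event review in 13.3 names seriousness and relationship but not outcome. Monitoring may inspect source data and the database (14, 17), but it would check the coding against these same definitions.

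**Working it through.** No figure in the documents depends on the outcome codes, so there is nothing to recompute. The sample size in 16.1 concerns fracture healing and does not use them. The check is to take the possible states of an event at the last record and ask which definitions each one meets as written.

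| State at last record | Definitions met | Status after the 13.5.6 note, if serious |
|---|---|---|
| A. Over, nothing left behind | *Resolved* | *Resolved* |
| B. Over, residual pathology | *Resolved with Sequelae* (the more specific code; 13.5.1 is also met) | *Resolved with Sequelae* |
| C. Partly improved, still present, still improving | *Resolved* and *Resolving* | *Resolved* or *On-going* |
| D. Partly improved, still present, plateaued | *Resolved*; *Resolved with Sequelae* only if the subject is held to have recuperated | *Resolved* (or *Resolved with Sequelae*) |
| E. No improvement | *Not Resolved* | *On-going* |

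Rows A, B and E cause no difficulty. The problem lies in C and D.

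**Row C.** The event has improved, which satisfies 13.5.1. It is improving, which satisfies 13.5.3. It fails 13.5.4, because that code needs the absence of improvement. Two codes fit, and the note in 13.5.6 sends them to different statuses: one closed, one open.

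**Row D.** The event is no longer improving, so 13.5.3 does not fit. It has improved, so 13.5.4 does not fit. Its state is known, so *Unknown* does not fit. What remains is 13.5.1, or 13.5.2 if one argues that the subject recuperated. Both are closed statuses. Read literally, the text gives a persisting, plateaued event no route to *On-going*.

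So in row C the text permits either status, and in row D it points to a closed status although the event is still present.

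**The case against.** **Tense separates the terms.** *Resolved* speaks of improvement completed and *Resolving* of improvement under way. Section 12.4.8 also asks that records ideally carry a resolution date, and an event still under way would not have one. This is a fair reading and would settle many row C cases in practice. It does not help row D, where improvement has stopped and the event remains. And if improvement in 13.5.1 is meant as full recovery, the word adds nothing to recuperation and can go.

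***Resolved with Sequelae* already covers incomplete recovery.** It does for events that have ended and left residual pathology, and any correction must respect that. It requires that the subject recuperated, so it does not clearly take an event that is only partly better and still present. The boundary needs stating.

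**The endpoint is not affected.** This stands. The secondary endpoint in 10.8.2 concerns the incidence and frequency of complications and adverse events and their relation to implant, instrumentation or procedure. The outcome code changes none of these. Section 16.2 plans frequencies and percentages for complication data and names no resolved proportion. No test or threshold rests on it.

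**Stronger readings.** A reader might infer that the safety results are biased in the device's favour. The wording does allow too many events to be called resolved, but the documents do not show how investigators would code them, and the note in 13.5.6 is cautious with *Resolving*, *Not Resolved* and *Unknown*. A reader might also try to attach a figure by assuming a number of complications and a fraction that only partly recovered. The documents supply neither, so the result would merely restate the assumption.

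**Conclusion.** The point holds as a defect in a coding definition. As written, an event that has improved but is still present meets *Resolved*, may also meet *Resolving*, and cannot be *Not Resolved*. For serious events and device deficiencies, the same partial recovery can be reported as *Resolved* or *On-going*.

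The consequence is limited to the descriptive outcome summary under 12.4.8 and the status of serious events and device deficiencies in MDR reporting. Event incidence, seriousness, causality and the primary endpoint are unaffected. The number of events concerned cannot be estimated from the documents; it would be zero if no complication were left partly improved at the last record. The conclusion rests only on the ordinary meaning of the definitions, in particular that improvement and recuperation are offered as alternatives. This is a minor correction, worth making because it is cheap and because the outcomes must be reported.

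**What to change.** - **13.5.1:** delete 'improved or', so that *Resolved* requires recuperation.
- **13.5.3:** state that an event that has improved but is still present at the last record is *Resolving*, including one that has plateaued, and so *On-going* if serious. The plateau must be named, since the label alone would not suggest it.
- **13.5.2:** keep this code for events that have ended with residual pathology, so that ended or still present is the dividing line from *Resolving*.
- **13.5.4:** keep this code for no improvement.

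The codes are then separated before the note in 13.5.6 applies, and that note needs no change.

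The cost is a few words in the protocol, through the amendment procedure in section 20. No new data items are needed; any outcomes already coded *Resolved* would need checking against the new wording. The resolved proportion may be slightly less favourable.

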13.5.2 Resolved with Sequelae

This outcome indicates the subject recuperated but retained pathological conditions resulting from the prior disease or injury.

13.5.3 Resolving*

This outcome indicates that the event is improving.

13.5.4 Not Resolved*

This outcome indicates that the adverse event has not improved or recuperated.

13.5.5 Fatal*

The adverse event resulted in the termination of life.

13.5.6 Unknown*

The outcome of the adverse event is not known, not observed, not recorded, or patient refused to provide information to make an outcome determination.

*Per Regulation (EU) 2017/745 [3], all serious adverse events will be classified according to event status outlined in MDCG 2020-10/1 [4] when used to support MDR reporting requirements. These event statuses include Resolved, Resolved with Sequelae, Death,

and On-going. In order to comply with this reporting requirement, all serious adverse events or Device Deficiency (DD) with outcomes classified as 'Resolving', 'Not Resolved', or 'Unknown', will be reclassified as 'On-going' and all serious adverse events classified as 'Fatal' will be reclassified as 'Death'.

14 Monitoring

Prior to initiating the clinical study, the Sponsor may conduct a site evaluation visit to ensure the Investigator and study staff understands the study protocol and requirements and have adequate time and resources to implement and conduct the study. Prior to study initiation, EC approval and a fully executed CTA must be in place.

This is a post-market study that does not involve investigational products or procedures, and there is no physical risks to the patients to be included in the study. Many assessments, such as the Harris Hip Score were used as standard-of-care for this patient population and do not require special training for their use in the study. As such, site initiation visits may be conducted remotely for this study.

During the course of the study, the Sponsor would conduct periodic central monitoring if necessary and maintain contact with the study staff to monitor compliance and evidence of adverse events, in accordance with the Sponsor's policies and procedures. The Sponsor will address any identified non-compliance with the executed CTA, study protocol, and applicable regulatory requirements.

If onsite monitoring visit(s) are deemed appropriate by the Sponsor, the Investigator will permit representatives of the Sponsor's monitoring team to have direct access to inspect all source data/documents, study documents/binders, study subject forms, database, corresponding sections of study subject medical/hospital records, and any other documents relevant to the study.

Additional details are provided in the Monitoring plan.

15 Risk Analysis

A discussion of the different types of risks and benefits involved with participation in the investigation, including, but not limited to:

15.1 General

Since all patients have already been operated with the study device and data is only collected retrospectively, there are no anticipated risks specific to study participation. There are no experimental procedures in this study, and participation in this study is not anticipated to affect the medical treatment of included subjects.

When used in accordance with product labelling, the risks associated with the use of the Zimmer Reconstruction System are similar to those of standard, stainless steel systems used for the same

clinical indication or purpose. These risks are either surgical risks or risks associated with the subject procedure/study device. Unanticipated adverse events can also occur.

A list of adverse events (AE) and anticipated adverse device effects (ADE) can be found in the Instruction for Use of the system (see “Adverse Effects” section). Investigators should refer to it.

15.2 Indemnification

The indemnification provision is located in the Indemnification section of the executed CTA.

If an injury is caused to a patient as a result of procedures undertaken in accordance with the Study, the Sponsor is liable for damages resulting from the Study. Zimmer GmbH maintains product liability and excess liability insurance coverage through its parent company Zimmer Holdings, Inc.

16 Statistical Methods

16.1 Sample Size Calculation

The overall success rate of the Zimmer Reconstruction System will be calculated based on the percentage of subjects who have successful fracture healing. The following hypothesis will be tested by exact binomial test

$$\begin{aligned}H_0: E1 - E0 &\leq -\delta E \\H_a: E1 - E0 &> -\delta E\end{aligned}$$

Where:

$E0 = 90\%$, the expected success rate of similar devices to the Zimmer Reconstruction System [13]

$E1$ = the success rate in the Zimmer Reconstruction System treatment group

$\delta E = 0.10$, non-inferiority margin for fracture healing

In addition, one-sided 95% exact confidence Interval (CI), lower limit of the success rate, will be calculated.

The sample size was estimated based on the expected performance of 90% fracture union rate. The sample size includes a 10% non-inferiority margin ($90\% - 10\% = 80\%$). The expected Clinical Performance Rate of the Zimmer Reconstruction System is assumed as 90%.

Based on the hypothesis test above, a sample size of $n = 83$ will provide approximately 80% power for the one-sided exact binomial test at 0.05 significant level. The sample size was calculated using SAS for Windows version 9.4. The aim of this study is to include a total number of 83 cases treated between 2010 and 2018 with implants of the Zimmer Reconstruction System at the Azienda Ospedaliero Universitaria Senese in Siena, Italy.

16.2 General Statistical Methods

Data collected in the study will be summarized descriptively. Descriptive summaries will be the basis of study reports to participants, as well as to generate an overall summary of the clinical and radiological evaluation of the Zimmer Reconstruction System described in this protocol.

Continuous data (e.g. age) will be summarized through means, medians, standard deviation, minimum, maximum and 95% confidence intervals (CIs) over time periods of interest. Categorical data (e.g. gender) will be summarized using counts, percentages and 95% confidence limits over time periods of interest. Summaries of fracture healing rate and complication data will be presented as frequencies and percentages. Subgroup summaries will be generated as needed either by strata within the study population (e.g. male vs. female) or by different cut-points (e.g. body mass index (BMI) ranges).

17 Quality Control & Quality Assurance

The study is conducted in accordance with the ISO 14155:2020 [1] and the Declaration of Helsinki [2].

The Investigator will be required to permit representative(s) of the Sponsor's monitoring team to inspect the database and corresponding sections of the study patients' office records and/or hospital original medical records. These audits will be done for quality assurance purposes, i.e. verifying adherence to the Clinical Investigation Plan and the completeness and accuracy of the data being entered on the database.

The Clinical Investigation Plan will be provided to the participating study center. The Investigators will be fully trained in the proper reporting and submission of trial data prior to patient enrolment. The completion of the database, database data quality, and data queries management for missing or unclear data performed before the statistical evaluation is responsibility of the investigator, since the sponsor will have access only to anonymized final data.

There are regular meetings between the Investigators and Zimmer Biomet Clinical Affairs staff. Written correspondence to the site is used to inform the Investigators of routine study details and to update them on study status.

18 Suspension or Premature Termination of the Clinical Investigation

Zimmer Biomet may decide to suspend or prematurely terminate the clinical study at the investigational site if, for example, information becomes available that the data indicates that the results significantly differ from the study objectives or statistical endpoints.

In the case of an early termination of the study, the EC and regulatory authority(ies) should be informed in accordance with regional and/or national laws/regulations, and EC requirements. The reasons for termination should be provided and documented.

In case the study got suspended or prematurely terminated before a subject has been

included in the study, the study subject shall proceed according to the investigator's standard of care or hospital's standard procedures.

19 Vulnerable Populations (as applicable)

Patients that are within one or more vulnerable populations, including children and prisoners are to be excluded from this study. Due to the retrospective design of the study and the reporting of only anonymized data there is no need of a informed consent process, as decided by the EC.

20 Amendments / Modifications to the Clinical Investigation Plan

The use of waivers from the clinical protocol is prohibited. All amendments to this clinical protocol shall be agreed to by the Sponsor and be recorded with a justification for the amendment prior to implementation. Approval from the EC must be obtained prior to implementation of the amended protocol, if required by regional and/or national laws/regulations. In the case of an amendment to the protocol, the revision history will be documented in the Document History section of this protocol.

21 Publication Policy

Both the Principal Investigator and the Sponsor have the right to publish or allow the results of the clinical study to be published. The Principal Investigator recognizes that the Sponsor has a special interest in the results of the clinical study and will submit manuscripts or final reports to the Sponsor prior to publication. If the Sponsor desires changes to be made, these are communicated to the Principal Investigator within 30 days of submission. Pooled data may be used for training and meetings.

22 Signatures

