8.2 Exclusion Criteria

The exclusion criteria are:

- Off-label use
- Patients under the age of 18
- Severely comminuted fractures in which bone fragments are too small or numerous to adequately fix or maintain a reduced position
- Infection
- Metal sensitivity or intolerance
- Severe osteopenia and/or osteoporosis, or in the presence of marked or rapid bone absorption, metabolic bone disease, cancer, or any other tumor-like condition of the

bone which may compromise fixation

- Sternal or spinal fractures
- Anatomical location in which the device would interfere with nerves, blood vessels, or other vital structures
- Patients with inadequate soft tissue coverage at the implant site.

9 Study Objectives

This is a PMCF study to fulfil the post-market surveillance obligations according to Medical Device Directive, MEDDEV 2.12-2 and the Medical Devices Regulation (MDR 2017/745). The objective of this retrospective PMCF study is to collect data confirming safety, performance and clinical benefits of the Zimmer Reconstruction System (implant and instrumentation) when used for temporary internal fixation and stabilization of fractures during the normal healing process.

- Performance will be evaluated by assessing bone union radiographically and/or clinically
- Safety will be evaluated by monitoring the frequency and incidence of adverse events (AE), serious adverse events (SAE), adverse device effects (ADE), serious adverse device effects (SADE), unanticipated serious adverse device effects (USADE) and device deficiencies (DD). Relation of the events to implant, instrumentation and/or procedure should be specified.
- Clinical benefits will be determined by the Harris Hip Score recorded at the longest follow-up after surgery (at least 1 year post-operative).

10 Study Design and Endpoints

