10.7 Type and Timing of Observations

This study is designed to be retrospective. To avoid bias, consecutive series of cases will be identified and included in the study. The study duration is expected to be 12 months overall, which corresponds to time dedicated to the retrospective data collection from hospital charts from the pre-operative condition to the last consultation visit (at least 1-year post-operative), to conduct the analysis and to draft the final report.

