10.8.2 Secondary Endpoint

The secondary endpoint is the assessment of safety by recording and analyzing the incidence and frequency of complications and adverse events. Relation of the events to implant, instrumentation and/or procedure should be specified. Subjects' outcomes will also be assessed.

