11.9 Follow-up Procedures

Follow-up evaluation was conducted at a minimum of 1 year after surgery. Data collection will include but is not limited to the following:

- FUP date

- Fracture healing (union/non-union) evaluated by x-ray and/or clinically
- Pain and functional performance as reported by the Harris Hip Score (3)
- Adverse events and complications and date of its occurrence (relation to implant, instrumentation and/or procedure should be specified)
- Revisions/Implant removal date and reason (relation to implant, instrumentation and/or procedure should be specified)
- Study deviation, if any

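### Section 16.2 reports complications and revisions as crude percentages with no time horizon, although follow-up varies between cases and has no upper limit

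*Combined protocol and SAP*

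**What the plan says.** The secondary endpoint in section 10.8.2 is safety, assessed by "recording and analyzing the incidence and frequency of complications and adverse events". No period is given over which incidence is to be measured.

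Section 16.2 gives the analysis: "Summaries of fracture healing rate and complication data will be presented as frequencies and percentages". The sentence before it is more general: "Categorical data (e.g. gender) will be summarized using counts, percentages and 95% confidence limits over time periods of interest". Those periods are not defined anywhere, and the sentence on complications does not repeat them.

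Observation is open-ended. Section 11.9 states: "Follow-up evaluation was conducted at a minimum of 1 year after surgery". Section 10.7 describes chart data from the "pre-operative condition to the last consultation visit (at least 1-year post-operative" mark, and section 9 takes the Harris Hip Score as "recorded at the longest follow-up after surgery (at least 1 year post-operative". Sections 11.10 and 12.4.5 declare loss to follow-up not applicable, so censoring is not discussed.

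The dates that a time-based analysis needs are on the collection list: operation date (11.8), follow-up date, "Adverse events and complications and date of its occurrence" and "Revisions/Implant removal date and reason" (all 11.9). Section 12.4.2 has all revision surgeries reported as adverse events.

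**The concern.** A count of events divided by a count of cases treats a case last seen at 1 year and one last seen much later as equally observed. The result mixes the device's event risk with the length of the charts. Two series with the same underlying risk can give different percentages, and a reader cannot tell which part comes from which source.

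Enrolment adds to this. Under section 10.5 it starts with 2018 operations and works backwards until 83 cases are found. How far back the site has to go therefore influences how long cases could have been followed, and so influences the percentage.

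The plan also leaves little room for later repair. Under sections 12.2.1 and 12.2.2 the case-level database stays at the hospital, and the sponsor receives only an anonymized final report written on the sponsor's template. If that report contains only crude percentages, the sponsor cannot derive time-based risks from it.

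**Working it through.** **The plan's own figure.** The only design figure is for fracture healing, in section 16.1: about 80% power with n = 83, null rate 80%, true rate 90%, one-sided 0.05. The smallest count r with P(X ≥ r | 83, 0.80) ≤ 0.05 is 73. The exact type I error is then 0.0412 and the power 0.795, so the figure reproduces. It says nothing about safety. The documents state no complication rate, revision rate or follow-up distribution, so everything below is illustration under assumed values, shown as ranges.

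**Inputs from the documents.** Surgery 2010–2018 (10.5); follow-up at least 1 year with no maximum (10.7, 11.9); complications as percentages (16.2).

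**Assumed.** Follow-up uniform over 1–3 years (short) or 1–11 years (long), and two risk patterns.

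**Pattern A: constant hazard h per year.** Risk by time t is 1 − exp(−ht). With follow-up uniform from a to b, the crude percentage is

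1 − [exp(−ha) − exp(−hb)] / [h(b − a)].

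For h = 0.02:
- 1–3 years: 1 − (0.9802 − 0.9418)/0.04 = 3.9%.
- 1–11 years: 1 − (0.9802 − 0.8025)/0.20 = 11.2%.

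| h per year | risk at 1 year | risk at 10 years | crude, 1–3 years | crude, 1–11 years | ratio |
|---|---|---|---|---|---|
| 1% | 1.0% | 9.5% | 2.0% | 5.8% | 2.92 |
| 2% | 2.0% | 18.1% | 3.9% | 11.2% | 2.85 |
| 3% | 3.0% | 25.9% | 5.8% | 16.2% | 2.78 |
| 5% | 4.9% | 39.3% | 9.5% | 25.1% | 2.65 |

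**Pattern B: front-loaded risk.** Risk p1 in year 1, then constant hazard h. With follow-up uniform from 1 to b, the crude percentage is

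1 − (1 − p1) × [1 − exp(−h(b − 1))] / [h(b − 1)],

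and the share arising after year 1 is 1 − p1/crude.

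For p1 = 0.10, h = 0.01, b = 11: 1 − 0.90 × 0.9516 = 14.4%, and the late share is 1 − 0.10/0.1435 = 30%.

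| p1 | h per year | crude, 1–3 years (late share) | crude, 1–11 years (late share) |
|---|---|---|---|
| 5% | 0.25% | 5.2% (4.5%) | 6.2% (19.1%) |
| 5% | 2% | 6.9% (27.3%) | 13.9% (64.0%) |
| 10% | 1% | 10.9% (8.2%) | 14.4% (30.3%) |
| 15% | 0.25% | 15.2% (1.4%) | 16.1% (6.6%) |
| 15% | 2% | 16.7% (10.1%) | 23.0% (34.7%) |

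The full grid was p1 = 5, 10, 15% by h = 0.25, 0.5, 1, 2%. Over it the late share ran from 1.4% to 27.3% for short follow-up and from 6.6% to 64.0% for long. It exceeded one half in only one of the 24 combinations. The ratio of long to short crude percentages ran from 0.1605/0.1521 = 1.06 to 0.1390/0.0687 = 2.02.

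**The case against.** The strongest reply is that early events may dominate. The device gives temporary fixation while a fracture heals, operative and immediate post-operative events are collected separately (11.8), and every case is meant to have at least 1 year of observation. If most events fall in that year, length of follow-up changes the percentage only modestly, as pattern B shows. This stands, and several stronger readings must be set aside because of it and related points:

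- A reader might infer that the safety percentages mostly reflect length of follow-up. That needs a late hazard that the documents do not give.
- A reader might infer follow-up of a decade or more. That is only a possible maximum, drawn from 2010 surgery and a protocol citing a 2020 standard. Enrolment runs backwards from 2018 and may stop well before 2010, and observation ends at the last recorded visit.
- A reader might infer that the percentages cannot be compared with any benchmark. They are hard to compare, but the plan sets no safety benchmark or test, and percentages shown with the follow-up distribution can be interpreted.
- A reader might infer that complete dates are assured. Section 12.4.8 asks for date of onset only as an ideal.

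It can also be said that section 16.2 does refer to periods of interest. This softens the point without answering it. The periods are undefined, and the only interval after the immediate post-operative one in the section 5 schedule is the last visit, which is itself open-ended.

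Finally, censoring at the last consultation may be informative: patients with problems may keep returning while well patients stop. That is a real limit on later estimates, but not a reason to prefer a percentage with no time basis.

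**Conclusion.** The concern holds in this form: the planned complication and revision percentages have no defined time basis, so they depend on follow-up length as well as on the device and do not estimate incidence.

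The size cannot be fixed from the documents. It may be small (crude percentages 1.06 times apart with strongly front-loaded risk) or large (about 2.7–2.9 times apart under a constant hazard). Both results rest on assumed event rates and on uniform follow-up over 1–3 and 1–11 years. The plan as written would not let a reader of the final report tell which applies.

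The point concerns a descriptive secondary endpoint. The primary healing analysis, the sample size and any decision rule are unaffected. It should be corrected because the correction is cheap and the sponsor could not make it from the final report.

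**What to change.** In section 16.2 and the final report template, for revision, implant removal (by reason) and each main complication category:

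1. Report the proportion of cases with an event by 12 months, with a 95% CI.
2. For later events, report Kaplan-Meier or cumulative-incidence estimates (death as a competing event) while enough cases remain at risk, or events per 100 case-years.
3. Report the median and range of follow-up beside these figures.
4. Keep the crude counts as a listing.
5. State how many event dates are missing, and that censoring at last consultation may be informative. Because section 11.4.2 counts each fractured site as a case, also say whether the intervals allow for several cases in one patient.

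Whether cases with less than 1 year of follow-up should be included is a separate eligibility question that this change does not settle.

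The cost is a paragraph in section 16.2, a table in the template and slightly more analysis work. The required dates are already on the collection list, though some may prove incomplete in the charts.
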